9.4.2 Assessment of Severity

Reportable AEs will be graded according to Common Terminology Criteria for Adverse Events (CTCAE) Version 4.0, published May 28, 2009 (v.4.03 June 14, 2010). The severity of each event will be classified into one of five defined categories as follows:

- Grade 1 Mild
- Grade 2 Moderate
- Grade 3 Severe
- Grade 4 Life Threatening or Disabling
- Grade 5 Death

9.4.3 Assessment of Relationship to Study Product or Procedure

Relationship to Study: The clinician's assessment of an AE's relationship to study product or study procedures is part of the documentation process and may determine what is or is not reported in the study (Please see CAPSIL definition of an AE). If there is any doubt as to whether a clinical observation is a reportable AE, the event should be reported. Reportable AEs must have their relationship to study product or procedure assessed using the terms: related or not related. To help assess, the following guidelines are used.

- Related – There is a reasonable possibility that the study product or study procedure caused the adverse event. Reasonable possibility means that there is evidence to suggest a causal relationship between the study product or study procedure and the adverse event.
- Not Related – There is not a reasonable possibility that the study product or study procedure caused the adverse event.

The investigator must provide an assessment of relationship of AEs to the study product based on:

- Temporal relationship of the event to the administration of study product or procedure
- Whether an alternative etiology has been identified

- Biological plausibility
- Existing therapy, and/or concomitant medications.

9.5 Reporting Interval

Site investigators will be responsible to monitor, document reportable AEs and SAEs, through study intervention period of the CAPSIL study plus one week. This is anticipated to be study day107 in the prophylaxis group and may vary in the preemptive group depending on treatment for viremia detected during study days 1-100.

Reportable AEs and SAEs will be followed until resolution, even if this extends beyond the study-reporting period. Resolution of an AE is defined as the return to pretreatment status or stabilization of the condition with the expectation that it will remain chronic.

At any time after completion of the study, if the investigator becomes aware of an SAE that is suspected to be related to study product, the investigator will report the event as a SAE.

9.6 Regulatory Reporting for Studies Conducted Under DMID-Sponsored IND

Following notification from the investigator, DMID, the IND sponsor, will report any suspected adverse reaction that is both serious and unexpected. DMID will report an adverse event as a suspected adverse reaction only if there is evidence to suggest a causal relationship between the drug and the adverse event. DMID will notify FDA and all participating investigators (i.e., all investigators to whom the sponsor is providing drug under its INDs or under any investigator's IND) in an IND safety report of potential serious risks from clinical trials or any other source, as soon as possible, but in no case later than 15 calendar days after the sponsor determines that the information qualifies for reporting as specified in 21 CFR Part 312.32. DMID will also notify FDA of any unexpected fatal or life-threatening suspected adverse reaction as soon as possible but in no case later than 7 calendar days after the sponsor's initial receipt of the information. Relevant follow-up information to an IND safety report will be submitted as soon as the information is available. Upon request from FDA, DMID will submit to FDA any additional data or information that the agency deems necessary, as soon as possible, but in no case later than 15 calendar days after receiving the request.

All reportable serious events designated as "not related" to study product(s), will be reported to the FDA at least annually in a summary format.

9.7 Reporting of Pregnancy

If pregnancy is discovered during the follow-up period the investigator must report information using the Pregnancy Report Form to the Coordinating Center. All pregnancies will be followed up to final outcome, using the pregnancy follow-up form. At that time, the status of the mother and infant will be noted, including the date of delivery and the infant's gender and weight.

The outcome, including any premature termination, must be reported to the Coordinating Center within calendar 5 days awareness of pregnancy on a pregnancy notification form. The pregnancy is not considered an AE; however pregnancy complications, including miscarriage or spontaneous abortion, are considered AEs. The report of any pregnancy and the outcomes of pregnancy as outlined above will be reported by the Coordinating Center to the DMID Medical Monitor within 7 business days of receiving pregnancy report form from the site.

9.8 Safety Monitoring By the DMID Safety Oversight Mechanism

9.8.1 Data and Safety Monitoring Board

A Data and Safety Monitoring Board (DSMB) will be established by the DMID. The DSMB members will consist of persons independent of the investigators or study team with no financial, scientific or other conflict of interest with the study and will be selected by the NIH. The initial responsibility of the DSMB will be to review and make recommendations regarding the initiation of the study. After the initiation of the study and during the course of the study at intervals determined by the DMID, the DSMB will:

1. Review the research protocol, template informed consent document and plans for data and safety monitoring.
2. Evaluate the progress of the study, including periodic assessments of data quality and timeliness, participant recruitment, accrual and retention, participant risk versus benefit, performance of the trial sites, and other factors that can affect study outcome.
3. Review study endpoints for differences between groups
4. Consider factors external to the study when relevant information becomes available,
5. Monitor the confidentiality of the study data and the results of monitoring.

The coordinating center will provide all data, tables, unique and repeated listings, figures, descriptive statistics, and tests of significance requested by the NIH for all DSMB meetings, interim analysis plan and final analysis.

9.8.2 Discontinuation of Study Enrollment and Study Product Administration for all Subjects in the Study

DMID, when it is the study sponsor, may interrupt study dosing and/or study entry at any time if medically indicated. To minimize risk, the medical monitor and the DSMB will review cumulative safety data. The study enrollment and dosing will be stopped, and an ad hoc review will be performed if halting rules are met.

9.8.3 Halting rules

1. All-cause mortality compared at interim analysis will be used as safety parameter for halting the trial. With 60 subjects enrolled, a difference in survival probability of greater than 37% would be detected at the .05 level with 90% power. Thus an important difference in mortality between the two groups if documented will be detected at interim analysis and DSMB recommended action can be undertaken. The table below depicts minimal detectable hazard ratio with sample size of 60.

Safety endpoint			
At interim-Minimal detectable hazard ratio with sample size of 60 at alpha=.05, power=.9:			
Probability of survival (inferior regimen)	Probability of survival (superior regimen)	Events	Hazard ratio
.600	.976	13	.048
.550	.950	16	.089

2. Halting for a difference in reportable SAEs will be done upon the recommendation of the DSMB if there is a statistically significant difference in reportable SAEs at the .05 level after at least 20 subjects are enrolled.

3. A statistically significant difference ($p=0.001$) of more than 50% between the two groups in the incidence of CMV disease after 1 year follow of 60 subjects.

10 END-POINTS COMMITTEE (EPC)

10.1 Composition

An EPC will be established comprising three individuals with expertise in CMV and transplantation to adjudicate CMV disease events. The members of the EPC will be independent of the study investigators and will be selected by the DMID. The function of the committee will be to review the supporting clinical and laboratory data from all subjects identified as having developed CMV disease by the site investigators. Based on their review of the protocol definition of CMV disease and the clinical and laboratory documentation, the committee will identify those CMV disease events that should be included in the primary efficacy analysis. The EPC members will receive no financial incentives for their participation, but may be reimbursed for customary consultative or administrative support fee as determined appropriate by the DMID.

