4. STUDY DESIGN

This is a /prospective, randomized, multicenter trial of prophylaxis versus preemptive therapy for the prevention of CMV disease in R-/D+ liver transplant subjects. Subjects meeting study criteria and who have provided informed consent will be randomized within 10 days post-transplant to receive, in an open label design, either prophylaxis with valganciclovir 900 mg once daily for 100 days or preemptive therapy (weekly monitoring for CMV viremia by plasma PCR weekly for 100 days post-randomization with initiation of valganciclovir 900 mg twice daily at onset of CMV viremia and continued until plasma PCR is negative on two consecutive weekly PCR tests). All dosages will be adjusted for renal dysfunction. Subjects will be followed during the intervention period (100 days post randomization) and until 12 months post-transplant for CMV disease, toxicity, and clinical outcomes (opportunistic infections, rejection, graft loss, retransplantation and mortality).

All-cause mortality, rejection episodes, graft loss and retransplantation, opportunistic infections (bacterial, fungal), need for dialysis, and post-transplant malignancies will be assessed until study closure (7 years from enrollment maximum).

Additionally, the impact of the two CMV prevention strategies on CMV-specific cellular and humoral immune responses will be evaluated at 100 days after randomization, and 6 and 12 months post-transplant.

It is anticipated that ~20-22% of all liver transplant recipients will belong to the R-/D+ group and will qualify for the study. Approximate time to enrollment will be 3.5 years. A minimum of 176 subjects will be enrolled in the study. Allowing for over-enrollment to replace dropouts, up to 205 subjects may be enrolled to achieve the target enrollment of 176 (see section 5.4.3.3). There will be a single interim analysis for the primary endpoint of CMV disease as adjudicated by an independent End Points Committee. This analysis will be conducted after~ 60 subjects have been enrolled and followed for 1 year. Study closure will occur 2 years after the enrollment of the last subject.

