7.7.3 Study day 1 through one year

Outcome data recording

After randomization and throughout the entire study period, all subjects will be followed and data collected related to study outcomes. All evaluations monitored will be completed as standard of care and not specifically for the study. Data collection and follow-up will be primarily achieved by medical record review at each study visit time point. Record reviews will include transplant hospital, out-patient clinics, outside hospitals, skilled nursing centers, and rehabilitation hospital records. Non-study hospital physicians and/or subjects may be contacted to verify whether or not they have had any additional hospitalizations or clinic visits outside of the transplant hospital in order to confirm complete collection of all outcome data.

Specific outcome data to be followed and recorded include:

- Evaluations for suspected and confirmed CMV disease
- All treatments for suspected and confirmed CMV disease
- Evaluations for organ rejection
- All treatments for organ rejection
- Graft loss and need for liver retransplantation
- Fungal, major bacterial, and non-CMV viral infections
- All-cause mortality during the 12 month
- All immunosuppressant taken during 100 days
- Immunosuppressant given for the treatment of rejection episodes for the 12 month period
- Immunosuppressant medication levels taken as standard of care
- Hospitalization status

7.7.4 Adverse Event Monitoring and Reporting (Study day 1 through 7 days post end of study treatment phase)

All subjects will be assessed for adverse events throughout the administration of drug period plus 7 days. This is anticipated to be study day 1 through 107 for prophylaxis group subjects. Preemptive therapy arm monitoring of AEs timelines will be individually determined based on the length of treatment for viremia detected during study days 1-100. Please see adverse event section for complete description of adverse event monitoring and reporting.

7.7.5 Study Specific Medication Compliance Visit (Study day 30, 60, and end of treatment +14 days)

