10.2 Responsibilities and Data Flow

The role of the EPC will be to evaluate and determine if the cases reported as having CMV disease by the investigators meet the protocol definition of CMV disease. In order to do so, the EPC will review all supporting clinical and laboratory data from such cases. The committee members will be blinded to the treatment allocation of all subjects in the study, including the subjects on which they are adjudicating. Subjects will be identified only with their study number. For the purposes of review, the following specific information will be provided to the EPC for the cases:

- Narrative summary that includes description of all signs and symptoms of the illness, and the reasons that the investigator diagnosed or suspected CMV disease.
- Type of CMV disease (viral syndrome or tissue invasive disease)
- Sites of CMV organ disease.
- Laboratory assay(s) that detected CMV disease
- Biopsy findings (if applicable)
- Other relevant laboratory, imaging studies or diagnostic procedures
- Outcome of disease and treatment employed.

The coordinating center will provide the required documents to the EPC. The EPC event adjudication will occur prior to interim analysis and prior to close out. It is anticipated that there will be approximately 30 CMV disease events to be reviewed.

The EPC will provide the coordinating center and the DMID with the conclusion for all cases that it has reviewed and whether the event meets the protocol definition of CMV disease (yes or no). When a unanimous decision cannot be made on the adjudication of the case by the three committee members, a vote will be taken and the majority vote will hold.

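### The blinded endpoint committee reviews only cases that unblinded sites report as CMV disease, so it can remove false positives but cannot recover missed cases

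*Combined protocol and SAP*

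**What the plan says.** Section 4 randomizes subjects to receive, "in an open label design, either prophylaxis with valganciclovir 900 mg once daily for 100 days or preemptive therapy". Sections 5.1 and 7.1 add that site investigators are also the subjects' care providers.

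The EPC is the blinded element: "The committee members will be blinded to the treatment allocation of all subjects in the study" (10.2). Under 10.1 it will "review the supporting clinical and laboratory data from all subjects identified as having developed CMV disease by the site investigators". Under 10.2 its role is to "determine if the cases reported as having CMV disease by the investigators meet the protocol definition of CMV disease". It returns a yes or no on the cases it has reviewed, and the plan anticipates "approximately 30 CMV disease events to be reviewed".

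The trial records more than it adjudicates. Section 7.7.3 lists "Evaluations for suspected and confirmed CMV disease" among the outcome data, together with treatments for suspected disease. Section 7.6.4 sends a central PCR sample for any subject in either arm whom the clinician or investigator suspects of having CMV disease.

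Section 12.5.1 defines the primary endpoint as disease adjudicated by the committee and/or determined by the investigator. Section 12.5.6 repeats the primary analysis separately for each source.

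**The concern.** Blinded adjudication is the main protection for an open-label primary endpoint that includes a clinical syndrome. Here the entry decision is made by someone who knows the arm, and the committee can act only on what it is given.

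There is room for judgement. CMV syndrome (8.1.4.1) is viremia plus any one of fever, severe malaise, leukopenia, atypical lymphocytosis or thrombocytopenia. Appendix C lists fever, leukopenia and thrombocytopenia among the expected events after liver transplant. Surveillance also differs by arm. Only preemptive subjects have scheduled weekly PCR, with results returned to the site, and they start treatment on viremia at any level. Study PCR in the prophylaxis arm depends on suspicion. A viremic, febrile preemptive subject could be recorded as infection under treatment and not called disease. Equally, knowing about the viremia could prompt more calls of disease. Either pattern would carry through to the adjudicated endpoint.

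**Working it through.** **1. Is there another route to the EPC?** Reading the sections on case identification, sampling and adjudication together:

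- 10.1 and 10.2 both define the input as investigator-identified or investigator-reported cases.
- The case summary in 10.2 is to include "the reasons that the investigator diagnosed or suspected CMV disease". This describes the narrative for a case already reported and does not widen referral.
- 7.6.4, 8.1.4.3 and 8.2.4.5 (suspected disease) send samples to the central laboratory and say nothing of the EPC.
- 8.1.6 (complete record review) and 11 (monitoring) support data capture only.

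No second route, algorithmic trigger or review of non-cases is described. Adjudicated cases are therefore a subset of investigator-called cases. Both analyses in 12.5.6 start from that larger set, so an uncalled case is absent from each. If and/or in 12.5.1 means the union, the primary endpoint equals the investigator-called set and even the EPC's exclusions would not affect it.

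**2. The plan's own figure.** Section 12.1 gives 80 per group for 20% versus 5%, two-sided 0.05, 80% power. Exact enumeration of Fisher's test gives 79.3%. The Freedman log-rank formula with HR = ln(0.95)/ln(0.80) = 0.230 gives (1.960+0.842)² × (1.230/0.770)² ≈ 20.0 events, and 2 × 20.0/(2−0.80−0.95) ≈ 160 subjects. The design reproduces.

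**3. Sensitivity to uncalled cases.** Inputs: 88 per arm (minimum 176, section 4, allocated 1:1), two-sided 0.05 (12.4.1), and CMH as the primary test (12.5.4). I take CMH as unstratified, because 12.5.4 adds the stratified version as a repeat, and without continuity correction. The uncalled fractions m are assumptions.

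For x and y events in n = 88 per arm, with N = 176 and t = x + y:

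CMH = (x − t/2)² / [n²·t·(N−t) / (N²(N−1))], referred to chi-square on 1 df.

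The rejection probability is the sum, over all (x, y) with p ≤ 0.05, of Bin(x; 88, p₁)·Bin(y; 88, p₂), where the affected arm's rate is multiplied by (1 − m).

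*Preemptive cases only uncalled, equal true rates (chance of p≤0.05):*

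| True rate, both arms | m=0 | 10% | 25% | 50% |
|---|---|---|---|---|
| 20% | 4.8% | 6.1% | 13.6% | 45.9% |
| 10% | 5.0% | 5.6% | 8.9% | 23.4% |

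*Prophylaxis cases only uncalled, true 20% vs 5% (power):*

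| m=0 | 10% | 20% | 30% |
|---|---|---|---|
| 88% | 80% | 69% | 55% |

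**4. In counts.** At 88 per arm, 20% and 5% are about 18 and 4 events.

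- 18 vs 4: 7²/4.84 = 10.12, p=0.0015.
- 18 vs 9: 4.5²/5.747 = 3.52, p=0.061.
- 12 vs 4: 4²/3.657 = 4.375, p=0.036.
- 11 vs 4: 3.5²/3.45 = 3.55, p=0.060.

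So five uncalled preemptive cases separate 18 vs 9 from 18 vs 4. In the other direction, seven uncalled prophylaxis cases are needed before a true 18 vs 4 loses significance.

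**The case against.** The strongest reply is that the gap may be small in practice. Most syndrome criteria have numeric thresholds, and only severe malaise is plainly subjective. Tissue-invasive disease other than retinitis needs CMV detected in a specimen. Records are to be reviewed for all post-transplant intervals, and monitors see the medical and laboratory reports. Investigator-determined disease counts whether or not it meets the protocol definition, which permits inclusive reporting. All of this stands, and it lowers the plausible missed fraction. At 10% one-sided under-calling the false-positive rate barely moves. None of it opens a route to the EPC.

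Two stronger readings are tempting. A reader might infer that the result will be biased toward preemptive therapy; the documents do not support this, because known viremia could raise or lower calling in that arm. A reader might also infer that losing six prophylaxis cases overturns a positive trial. It does so with Fisher's exact test (12 vs 4, p=0.064), but the primary test is CMH, which gives p=0.036.

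A further fair point is that sending only suspected episodes would not be enough. The 7.6.4 sample depends on the same unblinded suspicion. Preemptive valganciclovir is given for viremia, not for suspected disease, and the syndrome has no tissue result. The fever-with-viremia example could pass all three triggers, so an objective trigger is needed as well.

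**Conclusion.** The point holds as a weakness in data flow. As written, blinded adjudication can only subtract cases, and no planned analysis would show the ones never submitted. The size and direction of any bias cannot be derived from the documents. The ranges above rest on assumed one-sided missed fractions, 88 per arm and an unstratified CMH test. They show that about 10% one-sided under-calling does little to type I error but costs about 8 points of power when it falls on the prophylaxis arm, and that 20% to 30% or more would matter in either direction. This does not make the trial uninterpretable. It is a cheap improvement to an incomplete safeguard.

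**What to change.** Amend 10.1 and 10.2 so that the coordinating center sends the EPC, whatever the site's diagnosis:

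- (a) every suspected-CMV episode already recorded: a 7.6.4 sample, an evaluation or treatment for suspected CMV disease, or a positive tissue result;
- (b) every episode in the recorded data with a positive CMV result in blood plus a recorded 8.1.4.1 finding, identified by the same rule in both arms.

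State in 12.5.1 that the EPC result defines the adjudicated endpoint, and reconcile its and/or wording with 10.1, which has the EPC identify the events for the primary efficacy analysis.

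The cost is more dossiers than the roughly 30 expected, for the existing three members, with no new visits or tests. The documents do not allow the extra number to be estimated. Trigger (b) will flag more preemptive subjects because only they have weekly PCR. It is also weaker once scheduled PCR ends, when it relies on tests that clinicians order. The EPC-added cases should therefore be reported by arm and trigger, and the primary analysis repeated without them.

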10.2 Responsibilities and Data Flow

The role of the EPC will be to evaluate and determine if the cases reported as having CMV disease by the investigators meet the protocol definition of CMV disease. In order to do so, the EPC will review all supporting clinical and laboratory data from such cases. The committee members will be blinded to the treatment allocation of all subjects in the study, including the subjects on which they are adjudicating. Subjects will be identified only with their study number. For the purposes of review, the following specific information will be provided to the EPC for the cases:

- Narrative summary that includes description of all signs and symptoms of the illness, and the reasons that the investigator diagnosed or suspected CMV disease.
- Type of CMV disease (viral syndrome or tissue invasive disease)
- Sites of CMV organ disease.
- Laboratory assay(s) that detected CMV disease
- Biopsy findings (if applicable)
- Other relevant laboratory, imaging studies or diagnostic procedures
- Outcome of disease and treatment employed.

The coordinating center will provide the required documents to the EPC. The EPC event adjudication will occur prior to interim analysis and prior to close out. It is anticipated that there will be approximately 30 CMV disease events to be reviewed.

The EPC will provide the coordinating center and the DMID with the conclusion for all cases that it has reviewed and whether the event meets the protocol definition of CMV disease (yes or no). When a unanimous decision cannot be made on the adjudication of the case by the three committee members, a vote will be taken and the majority vote will hold.

